3.2 Standard Implementation Period

After pharmacy participants are enrolled, they will then complete one or two 8-week "standard implementation" period(s), depending on the step to which they are randomly assigned. At the beginning of this period, they will be asked to complete a 30-minute online training about COVID-19 vaccine hesitancy counseling and watch a live or pre-recorded webinar (their choice) that provides up-to-date information about COVID-19 vaccinations and boosters. After completion of the training and webinar, participants will be asked to implement the vaccine hesitancy counseling intervention with 10 vaccine hesitant patients per 8-week period. Pharmacists will use Qualtrics or a paper survey to document the extent to which the intervention results in customers getting vaccinated. They will specifically document the number of customers they offered the intervention to, the number who refused, and the number who agreed to be vaccinated. No identifiable customer-level data will be provided by the pharmacies.

Additionally, during the standard implementation period(s), trained study staff will observe and rate counseling fidelity two times per month for each participating pharmacy. We will use a fidelity rating scale to assess fidelity of delivery of the intervention during 4-8 total observed intervention sessions per pharmacy (4 per 8-week period). Since pharmacists have reported difficulties getting patients to agree to be recorded, affecting data collection, we will use standardized patients (SPs) in lieu of real patient conversations. Two SPs will have a total of 8 standardized scripts, each expressing different concerns about the Covid vaccine. The project manager will schedule a 20-minute block with an SP and participating pharmacist and send a Zoom link. Pharmacists will be randomized to script and order of the presentation of two SP scenarios. On the Zoom call, SPs will enact two of their cases, to which the pharmacist will ideally respond with the ASORT intervention. The encounter will be recorded using the secure Express Dictate mobile or desktop app and later rated for counseling fidelity. SPs will meet with each pharmacist one time per month, portraying different personas each time.

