5.1 Primary Outcome

The primary outcome of fidelity is captured at the pharmacy level. For our primary analysis of the fidelity outcome, we will use linear mixed-effects models (LMM) to compare the level of fidelity between the two implementation approaches (standard approach vs. virtual facilitation). We will report point estimates for the group mean difference along with a 95% confidence interval. The model-building approach will follow four analyses steps: 1) an unadjusted before/after of the effect of the virtual facilitation approach (ignoring period/time effect); 2) the time period (i.e., steps/blocks) to examine if any potential intervention effect relates only to the intervention or also to an independent effect of calendar time; 3) an adjustment for potential pharmacy-level confounders, such as size and learning climate; and 4) the interaction between period and intervention effect.

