5.3 Power Analyses

For the primary outcome of fidelity, captured at the pharmacy level, we wish to compare the fidelity scores under standard implementation versus fidelity scores under virtual facilitation. We expect each pharmacy to have approximately 4 fidelity assessments per time period (i.e., a period of 8 weeks). A sample of 30 pharmacies in an incomplete stepped-wedge cluster-randomized design with six periods (five steps), and an average of 10 fidelity assessments per pharmacy yields a total sample size of 320 assessments, which achieves over 90% power to detect a difference between means of 0.53 with a standard deviation of 1 (i.e., moderate effect size). The test statistic is based on a two-sided Wald Z-test with $ICC = 0.6$ and $\alpha = 0.05$. Given that we will have repeated fidelity measures from the same pharmacists over time, we have specified a conservative ICC (which in a stepped wedge design does not impact power calculations significantly).

For the secondary outcome of effectiveness, we expect each pharmacy to identify approximately 10 vaccine-hesitant patients during each time period (i.e., a period of 8 weeks). A sample of 30 pharmacies in an incomplete stepped-wedge cluster-randomized design with six periods (five steps) and an average of 27 patients per pharmacy yields a total sample size of 800 patients, which achieves over 90% power to detect a difference between effectiveness proportions of 10%. The proportion of vaccine-hesitant patients accepting the vaccine during the virtual facilitation approach is assumed to be 15% compared to 5% under the standard implementation period. These estimates are based on a review of reported changes in vaccine acceptance for evidence-based vaccine hesitancy interventions⁴⁰. The test statistic is based on a two-sided Wald Z-test with $ICC = 0.05$ and $\alpha = 0.05$. We note that the actual sample size should exceed 800 patients since we expect pharmacies will continue to identify vaccine-hesitant individuals during the follow-up periods.

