8.2 Confidentiality of the data

A secure, online survey data collection (Qualtrics) will be used to collect participant survey data. For interviews, participants will be informed that they have the right to refuse audio recording; in such cases the interviewer will take notes. For recorded interviews, the interviewer (who will be UAMS affiliated) will upload each digital recording to a password-protected file on a secure server at UAMS. Audio files will be transcribed by a professional transcriptionist who is employed by UAMS. Audio files will be maintained on the secure UAMS Server until transcription is complete and transcripts are checked for accuracy, at which time they will be destroyed. Recordings for fidelity observations will be made using the secure mobile app Express Dictate, will be encrypted, and will be maintained in secure, password-protected software or on the UNC server until observation guides are completed; then, the recordings will be permanently deleted. Completed survey data will be maintained in the secure Qualtrics system at UNC. Transcripts will be analyzed with a qualitative software package, and the findings generated with this program will be kept in the study folder on the secure server. To further protect confidentiality, we will request that no participant be referred to by name or in any way that would allow a person to be identified during the interview. Should this occur inadvertently, the name would be redacted from the transcript.

De-identified data on rates of delivering vaccine hesitancy counseling and the number of hesitant individuals who received a vaccine will be sent to and used by the study team for analysis. All pharmacy participants are trained in HIPAA compliance by nature of their employment and will not introduce additional risk beyond the normal risk associated with clinician handling of personal health information. Data from pharmacies utilized to calculate quantitative implementation outcomes and effectiveness will be stored in secure, password protected file on a UNC Server. All data on fidelity and effectiveness will

be recorded in aggregate and no identifying or personal health information of customers will be collected.

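### Script and scenario order are randomised in 3.2 but absent from the primary model in 5.1, which costs some precision without biasing the estimate

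*Combined protocol and SAP*

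**What the plan says.** Section 3.2 describes how fidelity is observed: "Two SPs will have a total of 8 standardized scripts, each expressing different concerns about the Covid vaccine". A pharmacist meets a standardized patient (SP) once a month by video and works through two scenarios per call, so there are four ratings in each 8-week period. The allocation is random: "Pharmacists will be randomized to script and order of the presentation of two SP scenarios".

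Section 5.1 builds the linear mixed model for fidelity in four steps: an unadjusted before/after comparison; the addition of time period; "an adjustment for potential pharmacy-level confounders, such as size and learning climate"; and a period-by-intervention interaction. It does not say which step gives the primary estimate. Script, SP, order and rater appear in none of the steps, nor elsewhere in section 5.

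Both covariates named in step 3 are pharmacy characteristics. Learning climate belongs to a survey measure averaged to one score per pharmacy (4.3). Pharmacy size is also a stratification factor for the block randomisation (2.2).

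**The concern.** A rating can depend on which vaccine concern the SP raises. If some scripts are harder to handle than others, that variation sits in the residual of the primary model. Because the trial itself allocates script at random, adjusting for it is legitimate and easy to prespecify. The covariates in step 3 act on the between-pharmacy variance, most of which the pharmacy random effect already removes from a comparison made largely within pharmacies.

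The plan accepts encounter-level adjustment elsewhere: step 3 for the secondary outcome (5.2) includes the patient's age, race and gender. The primary outcome has no counterpart.

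At stake are the width of the primary confidence interval and protection against a chance excess of hard scripts in one condition.

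**Working it through.** **Inputs.** Section 5.3 gives 30 pharmacies, 4 ratings per pharmacy-period, 320 ratings, ICC 0.6, two-sided α 0.05, and power "to detect a difference between means of 0.53 with a standard deviation of 1". Figure 1 gives 2, 3, 3, 2, 3, 3 standard or facilitation periods for blocks 1–6, follow-up excluded. That is 16 block-periods × 5 pharmacies = 80 pharmacy-periods, and 80 × 4 = 320 ratings, as stated. Taking SD 1 as the total SD, the between-pharmacy variance is τ² = 0.6 and the within-pharmacy variance is σ² = 0.4.

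**Reproducing the stated power.** The model has fixed period effects and a random pharmacy intercept. The variance of the facilitation effect is the matching diagonal element of (X′V⁻¹X)⁻¹.

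- A period mean of 4 ratings has within-pharmacy variance 0.4/4 = 0.1. For a pharmacy with k periods, V⁻¹ = (1/0.1)(I − ρₖJ), with ρₖ = 0.6/(0.1 + 0.6k): ρ₂ = 0.4615 and ρ₃ = 0.3158.
- Blocks 1–3 and 4–6 form two identical waves with no shared treatment periods. For one pharmacy per block, the facilitation term contributes 0.5385 + 0.6842 + 0.7368 = 1.9595. Estimating the three period effects takes away 1.5277, leaving 0.4318.
- Information = 5 pharmacies × 2 waves × (1/0.1) × 0.4318 = 43.18, so SE = 1/√43.18 = 0.152.
- Power = Φ(0.53/0.1522 − 1.96) = Φ(1.52) = 93.6%. The claim of over 90% is confirmed.

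**Pharmacy covariates (step 3).** These can only reduce τ².

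| Share of τ² explained (assumed) | SE | Cut in variance | Power |
|---|---|---|---|
| 10% | 0.152 | 0.4% | 93.7% |
| 30% | 0.151 | 1.4% | 93.9% |
| 50% | 0.150 | 3.0% | 94.3% |
| 75% | 0.146 | 7.7% | 95.2% |

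**Script and order.** These act on σ². The documents give no script variance, so the share is an assumption shown over a range. The SEs include the cost of fitting 7 script terms and 1 order term. Half-width is 1.96 × SE, and power is Φ(0.53/SE − 1.96).

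| Share of σ² explained (assumed) | SE, fitted | 95% half-width | Power | Cut in actual variance of the estimate |
|---|---|---|---|---|
| none | about 0.154 | 0.302 | 93.1% | none (SE up about 1%) |
| 10% | 0.146 | 0.286 | 95.3% | roughly 5–9% |
| 20% | 0.138 | 0.270 | 97.0% | roughly 12–18% |
| 30% | 0.129 | 0.253 | 98.4% | roughly 20–29% |

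The unadjusted half-width is 1.96 × 0.152 = 0.298.

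The last column is a range because the rule for drawing scripts is not given. Its low end applies if the four scripts in a period are distinct and drawn afresh each period. Script mix is then partly balanced already, and the unadjusted interval is somewhat conservative. Repeat calculations under that rule gave about 11–12% and 17–20% in the last two rows, so the lower limits are approximate. The high end applies if scripts are drawn independently.

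**Order.** Every call has one first and one second scenario, so each complete pharmacy-period is balanced. The weight of order in the treatment estimate computes to zero. Adjusting for order can lower only the residual variance.

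**Validity.** In simulated trials with no treatment effect and script variance 0.08 (20% of 0.4), the test rejected 4.9% of the time without script and 5.3% with it. Both are close to 5%.

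**The case against.** The strongest reply is that nothing in the planned inference is wrong. Script is randomised, the test holds its level, the stated power is met without the change, and the gain rests on a variance share that the documents do not supply. All of that stands. It limits the point to efficiency.

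A reader might go further in four ways that the documents do not support.

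- **That the omission biases the facilitation effect.** Random allocation of script means that omission by itself costs only precision and leaves chance imbalance uncorrected.
- **That the model adjusts only for pharmacy-constant factors.** Calendar period enters at step 2 and varies within pharmacy. Step 3 also speaks of confounders rather than precision covariates, and adjusting for size is justified because it is a stratifier.
- **That encounter-level ratings will be lost.** Section 8.2 says fidelity and effectiveness data will "be recorded in aggregate and no identifying or personal health information of customers will be collected", but that sentence protects customers. Section 8 has study staff entering observation-guide data, and 5.3 counts individual assessments. The averaging in 4.1 applies only where a pharmacy has more than one pharmacist, and 2.3 plans one.
- **That rater should join the primary model.** The number of raters and their allocation are not given. If raters were associated with condition, fixed rater effects could cost precision. Section 4.1 already requires blinded raters trained to 80% agreement.

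The gain also depends on the variance structure. If pharmacy effects drift between periods (assumed cluster autocorrelation 0.8), power falls to 67%, and script explaining 10–30% of residual variance cuts the variance of the estimate by only 4–13%. The margin above 90% is then gone, so a smaller gain still has value.

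**Conclusion.** The point holds as a matter of efficiency. The trial randomises script and order, the primary model uses neither, and the pharmacy-level covariates it names cannot do the same work at ICC 0.6. Script explaining 10% of within-pharmacy variance would narrow the reported interval (SE 0.146) more than pharmacy covariates explaining half of the between-pharmacy variance (SE 0.150).

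The omission is certain from the text; the size of the gain is not. It rests on SD 1 being the total SD, a pharmacy effect constant over periods, four ratings in every pharmacy-period, an assumed script share of 10–30%, and an unstated rule for drawing scripts. Order contributes nothing to balance.

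**What to change.** - In 5.1, fit the linear mixed model to individual encounter ratings, without averaging across pharmacists. Include calendar period, script (fixed effect, 8 levels) and order in call, and name this as the model used for H1.
- Store script, SP, order and rater with each rating when it is made. Recordings are deleted once the observation guide is complete (7.3, 8.2). In three-period blocks, 3 × 4 = 12 encounters come from 8 scripts, so some scripts must recur. State the rule for drawing and reusing scripts.
- Keep pharmacy size as planned, because it is a stratification factor.
- Use rater only as a sensitivity adjustment, once the number of raters and their allocation are known.

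The cost is SAP wording, four database columns and about 8 degrees of freedom, with an SE about 1% larger if script has no effect. Design, sample size and participant burden do not change.

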5.2 Secondary Outcome

For the secondary outcome of effectiveness, we will use generalized linear mixed models (GLMM) to investigate whether pharmacies are more effective at addressing vaccine hesitancy during virtual facilitation when compared to standard implementation. The effectiveness outcome will be binary (vaccine-hesitant patient accepts vaccine after counseling = 1; vaccine-hesitant patient does not accept vaccine after counseling = 0). We will report the odds ratio estimate of accepting the vaccine after counseling for the virtual facilitation approach (facilitation versus standard) along with a 95%

confidence interval. The model-building approach for our secondary effectiveness outcome will follow four analysis steps: 1) an unadjusted before/after of the effect of the virtual facilitation approach (ignoring period/time effect); 2) the inclusion of time period (i.e., steps) to examine if any potential intervention effect relates only to the intervention or also to an independent effect of calendar time; 3) an adjustment for patient's age, race, and gender and potential pharmacy-level confounders, such as pharmacy size; 4) the possible interaction between time period and intervention. The impact of virtual facilitation on effectiveness could potentially change over time if vaccine acceptance rates increase with time and as pharmacists gain experience with counseling vaccine-hesitant patients. We aim to explore this question through the inclusion of an interaction between period/time and intervention effect in Model 4. Additionally, the intraclass correlation coefficients (ICC) will be estimated and reported, so this information will be available for power analyses for future investigations using similar designs and outcomes. In order to reduce potential bias, during the virtual facilitation period, pharmacists will be instructed to approach patients that they did not approach during the standard facilitation period, which is feasible given the large number of unvaccinated individuals in the communities in which RURAL-CP pharmacies are located.

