2 INVESTIGATIONAL PLAN

2.1 Study Design

This is an implementation science study. We will use a randomized clinical trial with an adapted stepped-wedge design and 30 rural pharmacies to determine the effectiveness and incremental cost-effectiveness of a standard implementation approach compared to the addition of virtual facilitation by a trained facilitator in support of the delivery of a COVID-19 vaccine hesitancy counseling intervention. Mixed methods will provide triangulation, expansion, and explanation of quantitative findings.

In the incomplete stepped wedge cluster randomized design, each pharmacy will begin in the standard implementation approach condition for one or two 8-week periods and then "crossover" to the virtual facilitation condition for one or two 8-week periods. Length of time in each condition depends on the "step" to which pharmacies are randomly assigned. Figure 1 depicts the "stairstep" study design and

pharmacy assignment. For blocks 1–4, we will continue to collect data during one 8-week follow-up period to evaluate the potential impact of the virtual facilitation approach on sustained intervention fidelity and effectiveness once virtual facilitation has been stopped.

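### The period-adjusted effectiveness odds ratio leans on about 5 concurrent standard-condition events; section 5.2 needs a named interval method, an absolute effect and a rule for follow-up patients

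*Combined protocol and SAP*

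**What the plan says.** Section 5.2 treats effectiveness as a binary patient outcome in a GLMM and commits to one effect measure: "We will report the odds ratio estimate of accepting the vaccine after counseling for the virtual facilitation approach (facilitation versus standard", with a 95% confidence interval. Four model steps follow: no time effect, then period, then patient and pharmacy covariates, then "the possible interaction between time period and intervention". The last step is described as exploration. No step is named as the test of H2. No interval method is given (the word Wald occurs only in section 5.3), and there is no rule for sparse cells.

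Section 5.3 plans the sample on the absolute scale: it is one "which achieves over 90% power to detect a difference between effectiveness proportions of 10" percentage points, where the proportion "accepting the vaccine during the virtual facilitation approach is assumed to be 15% compared to 5% under the standard implementation period". It assumes a two-sided Wald Z-test, alpha 0.05 and ICC 0.05. It also expects follow-up patients on top of the 800, but section 5.2 does not say how they enter the model.

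Section 4.2 defines effectiveness as a proportion. Section 2.1 gives as a purpose of the trial "to determine the effectiveness and incremental cost-effectiveness of a standard implementation approach", compared with adding facilitation.

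**The concern.** A stepped-wedge effect that is adjusted for period draws on periods in which both conditions are running. Figure 1 has few of these, and acceptance under standard implementation is expected to be low. On the logit scale this combination can give wide, lopsided intervals and, when a cell has no events, no finite estimate. The reader would also receive an odds ratio for a trial planned on extra people vaccinated per 100 counselled, without an interval on that absolute scale. At stake are the precision and readability of the H2 result, and whether step 4 can be reported as specified.

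**Working it through.** **1. The plan's own figure.** Figure 1 has 1+2+1+1+2+1 = 8 standard and 1+1+2+1+1+2 = 8 facilitation block-periods. With 5 pharmacies per block, and since "we expect each pharmacy to identify approximately 10 vaccine-hesitant patients during each time period", N = 16 x 5 x 10 = 800. This matches "an average of 27 patients per pharmacy yields a total sample size of 800 patients". The power figure depends on choices that the plan does not state. The Hussey-Hughes variance for the Figure 1 layout (ICC 0.05, two-sided Wald Z) gives:

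| Assumption | Power |
|---|---|
| Variance of the 5% rate used for both conditions | 92.5% |
| No period effects | 99.7% |
| Follow-up coded as facilitation (N = 1000) | 92-93% |
| Period effects, follow-up excluded, variance reflecting both rates | 69.5-70.7% |

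**2. Where the conditions overlap (Figure 1, follow-up excluded).**

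| Period | Standard | Facilitation |
|---|---|---|
| Oct-Nov 2023 | blocks 1, 2, 3 | none |
| Dec-Jan 2023-24 | block 2 | blocks 1, 3 |
| Feb-Mar 2024 | none | blocks 2, 3 |
| Aug-Sep 2024 | blocks 4, 5, 6 | none |
| Oct-Nov 2024 | block 5 | blocks 4, 6 |
| Dec-Jan 2024-25 | none | blocks 5, 6 |

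The concurrent standard cells hold 2 x 5 x 10 = 100 patients and 100 x 0.05 = 5 expected events. All standard cells together hold 400 patients and 20 events. Without the two concurrent cells, the Model 2 design matrix falls from rank 7 to rank 6, so the period-adjusted effect is not identified.

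**3. Hand check of Model 2.** Each overlapping season has 2.5 events in 50 standard patients and 15 in 100 facilitation patients. Ignoring clustering, the variance of the log odds ratio per season is 1/2.5 + 1/47.5 + 1/15 + 1/85 = 0.50. Over two seasons it is 0.25, so SE = 0.50. The planned odds ratio is (0.15/0.85)/(0.05/0.95) = 3.35, with log 1.21. Then 1.21/0.50 = 2.42, and power is about Phi(2.42 - 1.96) = 68%.

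**4. Simulated Model 2.** Random-intercept logistic fits with categorical period, 10 patients per pharmacy-period, no calendar trend, 2,000 trials per scenario. The pharmacy SD on the logit scale is 0.416 (ICC 0.05 on the latent scale) or 0.732 (ICC 0.05 on the proportion scale).
- Coverage of the 95% Wald interval is 96.2-96.5% at the planned effect and 96.8% under no effect, so type I error is 3.2%. With added pharmacy-by-period variance, type I error is 3.7%.
- At the planned effect, including the added-variance scenario, 0.3-0.5% of intervals lie wholly above the true value and 3.3-3.8% wholly below it.
- The median estimate is about 3.5, with a typical interval of about 1.2 to 10.
- Power is 66-70% in these runs and 64-71% across all runs. There is no finite estimate in 0.8-1.2% of these trials, and in about 1-2% across all runs.

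**5. Model 4.** With categorical period the fixed effects have rank 8, that is 6 periods plus 2 effects, one per overlapping season. An effect is infinite when its standard cell has no event. For one cell, 0.95^50 = 7.7%. For at least one of two independent cells, 1 - (1 - 0.077)^2 = 14.8%. With clustering the figure is 17.3% and 20.2% (the two SDs) and 23.1% (beta-binomial, ICC 0.05). It is about 41% if the standard rate is 3%, and about 4% if it is 8%.

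**6. Profile likelihood instead of Wald.** With 1,000 trials per scenario, power rises from 71% to 77% in one clustering scenario and from 64% to 72% in the other, and the tails become balanced. Type I error is 5.8-5.9%. The Monte Carlo SE is sqrt(0.05 x 0.95/1000) = 0.7 points, so this is compatible with 5% but does not rule out slight inflation. Part of the power gain is simply the larger size of the test.

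**7. Absolute scale.** A period-adjusted risk difference on the same layout has SE 0.040, so the 95% half-width is 1.96 x 0.040 = 7.8 points and power is 70-71%. The scale alone hardly changes power.

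**The case against.** Several points on the other side stand.

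- Planning on proportions and analysing with a logistic GLMM is ordinary practice, and 15% against 5% fixes an odds ratio too. Descriptive proportions are also planned, through section 5 and Table 1. What is missing is an adjusted difference with an interval, which is a reporting gap and not a contradiction.
- Model 4 is expressly exploratory, and its failure does not threaten H2. The 15-23% assumes categorical period. Section 5.2 fixes no coding, and a linear time term would avoid the infinite estimates at the price of assuming linearity.
- The count of 5 events does not apply to Model 1, which uses all 20 standard events. That is limited comfort, because Model 1 ignores calendar time and section 5.2 itself allows that acceptance may rise over time.
- If follow-up patients enter as a third level, the effect is identified even without the two concurrent cells (rank 8 of 8). Coverage is then 95.7-96.4% and power 90-92%, taking the follow-up rate as equal to the facilitation rate.
- Section 2.1 mentions incremental cost-effectiveness, but Aim 2 describes only cost and budget analyses. An adjusted risk difference would be useful there, but its absence from section 5.2 does not by itself undo Aim 2.

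A reader might infer that the H2 interval is invalid. The figures do not support that: its error rate is below nominal, and section 5.2 never commits to Wald. A reader might also infer that the odds ratio is materially overstated. Its mean is pulled up by near-separated fits, but the median log odds ratio is off by only about 0.03-0.07 at the planned effect.

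**Conclusion.** The point holds as a gap in specification. With follow-up excluded, the period-adjusted comparison leans on 100 concurrent standard patients and about 5 expected events. A default Wald interval would then be valid but mildly conservative and lopsided, with power of about 64-71%. The exploratory Model 4 would lack one of its two estimable effects in roughly one trial in four to seven. Section 5.2 gives no absolute effect with an interval, although section 5.3 was planned on one.

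It might seem to follow that a risk difference should replace the odds ratio as the main H2 estimate. The documents do not require this. The power gain would be negligible, and the change would swap a conditional effect for a marginal one and assume additivity.

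The figures assume the planned 5% and 15% rates, 10 patients in every pharmacy-period, categorical period, no calendar trend and normal pharmacy intercepts. The scale of the ICC is not stated, so both readings were used. The coding of follow-up patients matters most: it moves power between about 70% and about 90%.

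**What to change.** Amend section 5.2 before the data are analysed:

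1. Keep the logistic GLMM odds ratio as the H2 estimate, and specify a profile-likelihood interval with the matching likelihood-ratio test. If the estimate is infinite, report the finite lower limit.
2. Add a period-adjusted risk difference, standardised from the same model, with a 95% confidence interval.
3. Replace the Model 4 interaction odds ratios with two season-specific risk differences (Dec-Jan 2023-24 and Oct-Nov 2024), reported descriptively.
4. State whether follow-up patients are excluded, form their own level or count as facilitation, and restate the power in section 5.3 for that choice.

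The cost is SAP wording and some programming, with no new data. The likelihood-ratio test gained roughly 6 to 8 points of power in simulation (77 - 71 and 72 - 64), at a type I error of 5.8-5.9% instead of 3-4%. The descriptive season results give up a formal interaction test, which these cell sizes could hardly support.
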